## 16 Appendices

### 16.1 Study Information

#### 16.1.1 Protocol and Protocol Amendments

The following protocols, amendments, and amendment summaries are provided:

Protocol Amendment 2	14 Aug 2008
Protocol Amendment 1 Addendum 2 (for France)	08 Nov 2007
Protocol Amendment 1 Addendum 1 (Administrative Change)	20 Jul 2007
Protocol Amendment 1	02 July 2007
Protocol Addendum 3 (for Germany – additional changes)	01 Nov 2006
Protocol Addendum 2 (for Hungary)	28 Jul 2006
Protocol Addendum 1 (for Germany)	06 Jul 2006
Original Protocol	10 Feb 2006

### 3. SUMMARY OF REVISIONS

**SECTION: 9.7.5 Discontinuation and Tapering of Study Medication**

*Added (see bold text)*

Patients who discontinue early from the open-label extension study will have their study medication tapered over a 3-week period, reducing their daily dose by one-third per week. After tapering has been completed, patients should return to the site immediately, and complete all assessments and evaluations scheduled for Visit 5, if patient discontinued early during the first year of the open-label extension study, complete all assessments and evaluations scheduled for Visit 8 if patient discontinued early during the second year of the open-label extension study, complete all assessments and evaluations scheduled for Visit 11 if patient discontinued early during the third year of the open-label extension study, **and complete all assessments and evaluations scheduled for Visit 14 if patient discontinued early during the fourth year of the open-label extension study** (Refer to Study Flow Chart in Appendix A).

**REVISION:** Added a fourth year visit to this procedure.

**RATIONALE:** This will allow patients, who enrolled early during the trial, to remain in the open label extension study until the study drug, retigabine, is approved and commercially available, or until the program is discontinued.

**SECTION: 10.1 Study Flow Chart**

*Added (see bold text)*

- Study Visit 1 (at Month 1  $\pm$ 3 days).
- Study Visit 1a for Hematological Monitoring (at Month 2  $\pm$ 7 days)
- Study Visit 2 (at Month 3  $\pm$ 7 days).
- Study Visit 2a for Hematological Monitoring (at Month 4  $\pm$ 7 days)
- Study Visit 3 (at Month 6  $\pm$ 7 days).
- Study Visit 3a for Hematological Monitoring (at Month 8  $\pm$ 7 days)
- Study Visit 4 (at Month 9  $\pm$ 7 days).
- Study Visit 4a for Hematological Monitoring (at Month 10  $\pm$ 7 days)
- Study Visit 5 (at Month 12  $\pm$ 7 days).
- Study Visit 6 (at Month 16  $\pm$ 7 days).
- Study Visit 7 (at Month 20  $\pm$ 7 days).
- Study Visit 8 (at Month 24  $\pm$ 7 days).
- Study Visit 9 (at Month 28  $\pm$ 7 days).
- Study Visit 10 (at Month 32  $\pm$ 7 days).
- Study Visit 11 (at Month 36  $\pm$ 7 days).
- **Study Visit 12 (at Month 40  $\pm$ 7 days).**
- **Study Visit 13 (at Month 44  $\pm$ 7 days).**
- **Study Visit 14 (at Month 48  $\pm$ 7 days).**

**REVISION:** Added fourth year visits and procedures.

**RATIONALE:** This will allow patients, who enrolled early during the trial, to remain in the open label extension study until the study drug, retigabine, is approved and commercially available, or until the program is discontinued.

**SECTION:** **10.3 Safety Assessments**

*First paragraph, added (see **bold text**)...*

Post-void residual (PVR) bladder ultrasounds to assess urinary retention and the American Urological Association (AUA) Symptom Index to assess urinary voiding function will also be performed during the first, **second, third and fourth** year of the open-label extension study.

**REVISION:** AUA and PVR assessments will be performed at visits 8, 11 and 14.

**RATIONALE:** To extend the urinary safety assessments after the first year of the trial.

**SECTION:** **10.3.2 Physical and Neurological Examinations**

*Added (see **bold text**)*

A complete physical and neurological examination will be performed annually at Visit 5, Visit 8, 11 **and Visit 14**. Brief neurological examinations will be performed at all other study visits, including visits 1, 2, 3, 4, 6, 7, 9, 10, **12 and 13**.

**RATIONALE:** Added additional visits for a fourth year patient assessment.

**REVISION:** This will allow patients, who enrolled early during the trial, to remain in the open label extension study until the study drug, retigabine, is approved and commercially available, or until the program is discontinued.

**SECTION:** **10.3.3 Electrocardiograms**

*Added (see **bold text**)*

A 12-lead ECG will be performed at all study visits during the first year of the open-label extension study (Visits 1, 2, 3, 4, 5), and annually at Visits 8, 11 **and 14...**

**REVISION:** Added a fourth year visit for the ECG assessment.

**RATIONALE:** This will allow patients, who enrolled early during the trial, to remain in the open label extension study until the study drug, retigabine, is approved and commercially available, or until the program is discontinued.

**SECTION: 10.3.5 Post-Void Residual (PVR) Bladder Ultrasound**

*Added (see bold text)...*

A post-void residual (PVR) bladder ultrasound to assess urinary retention will be performed at Visits 1, 2, 5, **8, 11, and 14** during the first, **second, third, and fourth** year of the open-label extension study.

**REVISION:** PVR assessments will be performed at visits 8, 11 and 14.

**RATIONALE:** To extend the urinary safety assessments after the first year (i.e., at the end of each subsequent year) of the study.

**SECTION: 10.3.6 AUA Symptom Index**

*Added (see bold text)...*

An AUA Symptom Index to assess urinary voiding function will be performed at Visits 1, 2, 5, **8, 11, and 14** during the first, **second, third, and fourth** year of the open-label extension study.

**REVISION:** AUA assessments will be performed at visits 8, 11 and 14.

**RATIONALE:** To extend the urinary safety assessment after the first year (i.e., at the end of each subsequent year) of the study.

**SECTION: 10.15.3 Visit 8 (Month 24)**

*Added (See bold text)...*

Patients will return for Study Visit 8 (Month 24). At this visit, the following evaluations will be performed:

- Seizure Diary (collection / review of current diary and dispensation of new diary)
- Complete Physical and Neurological Exam
- Vital Signs (BP, HR, and Temperature) and Body Weight
- **AUA Symptom Index**
- **PVR Bladder Ultrasound**
- Clinical Laboratory Tests (Blood Chemistries, Hematology, Urinalysis including microscopy)
- Serum Pregnancy Test
- 12-lead ECG
- Adverse Events
- Concomitant Medication
- QOLIE-31-P Questionnaire (completed by patient)
- Open-Label Study Medication (collect returned medication and dispense new medication)

**REVISION:** AUA and PVR assessments will be performed at visit 8.

**RATIONALE:** To extend the urinary safety assessments after the first year of the study.

**SECTION:** 10.15.6 Visit 11 (Month 36)

*Added... (see **bold** text)*

Patients will return for Study Visit 11 (Month 36). At this visit, the following evaluations will be performed:

- Seizure Diary (collection / review of current diary and dispensation of new diary)
- Complete Physical and Neurological Exam
- Vital Signs (BP, HR, and Temperature) and Body Weight
- **AUA Symptom Index**
- **PVR Bladder Ultrasound**
- Clinical Laboratory Tests (Blood Chemistries, Hematology, Urinalysis including microscopy)
- Serum Pregnancy Test
- 12-lead ECG
- Adverse Events
- Concomitant Medication
- QOLIE-31-P Questionnaire (completed by patient)
- Open-Label Study Medication (collect returned medication and dispense new medication)

**REVISION:** AUA and PVR assessments will be performed at visit 11.

**RATIONALE:** To extend the urinary safety assessments after the first year of the study.

**SECTION:** *Added the following sections...*

**10.15.7 Visit 12 (Month 40)**

Patients will return for Study Visit 12 (Month 40). At this visit, the following evaluations will be performed:

- Seizure Diary (collection / review of current diary and dispensation of new diary)
- Brief Neurological Exam
- Vital Signs (BP, HR, and Temperature) and Body Weight
- Clinical Laboratory Tests (Blood Chemistries, Hematology, Urinalysis including microscopy)
- Adverse Events
- Concomitant Medication
- Open-Label Study Medication (Collect returned medication and dispense new medication)

**10.15.8 Visit 13 (Month 44)**

Patients will return for Study Visit 13 (Month 44). At this visit, the following evaluations will be performed:

- Seizure Diary (collection / review of current diary and dispensation of new diary)
- Brief Neurological Exam
- Vital Signs (BP, HR, and Temperature) and Body Weight
- Clinical Laboratory Tests (Blood Chemistries, Hematology, Urinalysis including microscopy)
- Adverse Events
- Concomitant Medication
- Open-Label Study Medication (Collect returned medication and dispense new medication)

**10.15.9 Visit 14 (Month 48)**

Patients will return for Study Visit 14 (Month 48). At this visit, the following evaluations will be performed:

- Seizure Diary (collection / review of current diary and dispensation of new diary)
- Complete Physical and Neurological Exam
- Vital Signs (BP, HR, and Temperature) and Body Weight
- AUA Symptom Index
- PVR Bladder Ultrasound
- Clinical Laboratory Tests (Blood Chemistries, Hematology, Urinalysis including microscopy)
- Serum Pregnancy Test
- 12-lead ECG
- Adverse Events
- Concomitant Medication
- QOLIE-31-P Questionnaire (completed by patient)

- Open-Label Study Medication (collect returned medication and dispense new medication)

**REVISION:** Added fourth year visits and procedures.

**RATIONALE:** This will allow patients, who enrolled early during the trial, to remain in the open label extension study until the study drug, retigabine, is approved and commercially available, or until the program is discontinued.

**SECTION:** **10.16 Tapering**

*Added (see **bold text**)*

During the first year, these patients should then return for a final visit to complete all assessments and evaluations scheduled for Study Visit 5. During the second year, these patients should then return for a final visit to complete all assessments and evaluations scheduled for Study Visit 8. During the third year, these patients should then return for a final visit to complete all assessments and evaluations scheduled for Study Visit 11. ***During the fourth year, these patients should then return for a final visit to complete all assessments and evaluations scheduled for Study Visit 14*** (Refer to Study Flow Chart in Appendix A).

**REVISION:** Added a fourth year visit for this procedure.

**RATIONALE:** This will allow patients, who enrolled early during the trial, to remain in the open label extension study until the study drug, retigabine, is approved and commercially available, or until the program is discontinued.

**SECTION:** **10.20 Early Termination**

*Added (see **bold text**)*

Patients who discontinue early during the first year of the open-label extension study will complete all assessments and evaluations scheduled for Study Visit 5. Patients who discontinue early during the second year of the open-label extension study will complete all assessments and evaluations scheduled for Study Visit 8. Patients who discontinue early during the third year of the open-label extension study will complete all assessments and evaluations scheduled for Study Visit 11 ***and complete all assessments and evaluations scheduled for Visit 14 if patient discontinued early during the fourth year of the open-label extension study*** (Refer to Study Flow Chart in Appendix A).

**REVISION:** Added a fourth year visit for this procedure.

**RATIONALE:** This will allow patients, who enrolled early during the trial, to remain in the open label extension study until the study drug, retigabine, is approved and commercially available, or until the program is discontinued.

**SECTION:** **Appendix A. Study Flowchart (REVISED)**

**REVISION:**

- a. Added AUA and PVR assessments at visits 8 and 11.
- b. Added fourth year visits (Visits 12, 13 and 14) and procedures.

**RATIONALE:**

- a. To extend the urinary safety assessments after the first year of the study.
- b. This will allow patients, who enrolled early during the trial, to remain in the open label extension study until the study drug, retigabine, is approved and commercially available, or until the program is discontinued.

## 5. LIST OF ABBREVIATIONS

AE	=	Adverse event
AED	=	Antiepileptic drug
ALT	=	Alanine aminotransferase
ANCOVA	=	Analysis of covariance
ANOVA	=	Analysis of variance
APD	=	Action potential duration
AST	=	Aspartate aminotransferase
AUA	=	American Urological Association
AUC	=	Area under the curve
$\beta$ -HCG	=	Beta human chorionic gonadotropin
BID	=	Twice a day
BMI	=	Body mass index
BP	=	Blood pressure
BUN	=	Blood urea nitrogen
CFR	=	Code of Federal Regulations
CGI	=	Clinical global impressions
CI	=	Confidence interval
$C_{max}$	=	Observed maximum plasma concentration
$C_{min}$	=	Observed minimum plasma concentration
CNS	=	Central nervous system
CPMP	=	Committee for Proprietary Medicinal Products
CRA	=	Clinical research associate
CRF	=	Case report form
CSR	=	Clinical study report
CT	=	Computerized tomography
CV	=	Curriculum vitae
CV%	=	Coefficient of variation
D-20443	=	Dihydrochloride salt of retigabine
ECG	=	Electrocardiogram
EDTA	=	Ethylenediaminetetraacetic acid
EEG	=	Electroencephalogram
EMA	=	European Agency for the Evaluation of Medicinal Products
FDA	=	Food and Drug Administration
GABA	=	Gamma aminobutyric acid
GCP	=	Good Clinical Practice
hERG	=	Human ether-a-go-go related gene

HPF	=	High power field
HR	=	Heart rate
ICF	=	Informed consent form
ICH	=	International Conference on Harmonization
IEC	=	Independent Ethics Committee
ILAE	=	International League Against Epilepsy
IND	=	Investigational New Drug
IRB	=	Institutional Review Board
ISE	=	Integrated Summary of Efficacy
ISS	=	Integrated Summary of Safety
ITT	=	Intent to treat
i.v.	=	Intravenous
IVRS	=	Interactive Voice Response System
LFT	=	Liver function test
MAOI	=	Monamine oxidase inhibitor
MedDRA	=	Medical Dictionary for Regulatory Activities
MRI	=	Magnetic resonance imaging
msec	=	Milliseconds
MTD	=	Maximum tolerated dose
N	=	Number of patients
NAT	=	N-acetyl transferase
pH	=	Hydrogen Ion Concentration
PK	=	Pharmacokinetics
PGI	=	Patient global impressions
p.o.	=	Oral
PP	=	Per protocol
PVR	=	Post-void residual (bladder ultrasound)
QD	=	Once a day
QoL	=	Quality of Life
QOLIE-31-P	=	Quality of Life in Epilepsy-Problems Questionnaire
QTc	=	QT correction
QTcB	=	Bazett's QT correction
QTcF	=	Fridericia's QT correction
QTcl	=	Individual patient's QT correction
RBC	=	Red blood cell
REB	=	Research Ethics Board
SAE	=	Serious adverse event
SAP	=	Statistical Analysis Plan
SD	=	Standard deviation

SEM	=	Standard error of the mean
SUDEP	=	Sudden Unexplained Death in Epilepsy
$t_{1/2}$	=	Half life
TdP	=	Torsade des Pointes
TEAE	=	Treatment-emergent adverse event
TID	=	Three times a day
UDPGT	=	UDP-glucuronosyltransferase
UDS	=	unscheduled DNA synthesis
UGT	=	uridine diphosphate-glucuronosyltransferase
ULN	=	Upper limit of normal
URI	=	Upper respiratory infection
UTI	=	Urinary tract infection
Valeant	=	Valeant Pharmaceuticals, North America
VNS	=	Vagal nerve stimulator
WBC	=	White blood cell
WHO	=	World Health Organization

**6. STUDY SYNOPSIS**

TITLE:	A multicenter, open-label, long-term, safety, tolerability and efficacy study of retigabine in adult epilepsy patients with partial-onset seizures (Extension of Study VRX-RET-E22-302)
PHASE:	3
OBJECTIVES:	
 
1. Primary: To evaluate the safety and tolerability of long-term therapy with retigabine administered as adjunctive therapy in adult epilepsy patients with partial-onset seizures, who completed the double-blind Study VRX-RET-E22-302.
 
2. Secondary: To evaluate efficacy of long-term treatment with retigabine and patient quality of life, evaluated through the QOLIE-31-P questionnaire.
 

STUDY DESIGN:	This is an open-label extension study of the placebo-controlled, double-blind Study VRX-RET-E22-302. Patients will be treated with 600-1200 mg/day of retigabine as an adjunct therapy to their current antiepileptic medications (AEDs) or vagal nerve stimulation as established in Study VRX-RET-E22-302. Treatment will be continued until retigabine is approved and commercially available, or until the program is discontinued, followed by a 3-week tapering period and a 30 day post study period for collection of Adverse Events (AEs).
SAMPLE SIZE:	All patients who complete Study VRX-RET-E22-302 are qualified to participate (up to approximately 510 patients).
NUMBER OF SITES:	This is a multicenter study involving approximately 55-60 study sites in the Western, Central, and Eastern Europe, Australia, Israel, South Africa and the United States.
TREATMENT GROUPS:	All patients will be treated with 600-1200 mg/day of retigabine as an adjunct therapy to their current antiepileptic medications (AEDs) or vagal nerve stimulation.
TREATMENT DURATION:	This study will allow the patients who complete Study VRX-RET-E22-302 to continue with retigabine until the drug is approved and commercially available, or until the program is discontinued.
FORMULATION:	Retigabine will be supplied by Valeant Pharmaceuticals, North America in bottles containing tablets in relevant strengths: 50 mg, 100 mg, or 300 mg.


KEY INCLUSION CRITERIA:
	
 
1. Patient has successfully completed the Maintenance and Transition phases of Study VRX-RET-E22-302 for the treatment of partial-onset seizures
 
2. Patient is expected to benefit from participation in the study in the opinion of the Investigator.
 
3. Women of childbearing potential and fertile males have to agree to use a medically acceptable method of birth control. Females must have a negative urine pregnancy test at Visit 0, which will be confirmed by the serum <math>\beta</math>-HCG pregnancy test at the last visit (Visit 11) of the Transition phase of Study VRX-RET-E22-302. A woman of childbearing potential is defined as a female who is biologically capable of becoming pregnant. A medically acceptable method of birth control includes an intrauterine device in place for at least 3 months, surgical sterilization (e.g. tubal ligation), or adequate barrier methods (e.g., diaphragm and foam). An oral contraceptive alone is not considered adequate for the purpose of this study.
 
4. In the opinion of the Investigator, patient is able to understand verbal and written instructions and will adhere to all study schedules and requirements.
 
5. Patient or legal guardian (if applicable) is informed, given ample time and opportunity to read and/or understand about his/her participation in the study, and has signed and dated the written informed consent form.
 

KEY EXCLUSION CRITERIA:
	
 
1. Patient meets any of the withdrawal criteria in the previous VRX-RET-E22-302 study or is experiencing an ongoing serious adverse event.
 
2. Patient is receiving any investigational drug or using any experimental device in addition to Retigabine for treatment of epilepsy or any other medical condition.
 
3. Patient has any other condition that would prevent compliance with the study procedures or proper reporting of AEs.
 
4. Female patient who has a positive pregnancy test at any time during the study.
 


EVALUATION CRITERIA:
	
 
• Efficacy: Patients will keep a seizure diary throughout the study. The anticonvulsant efficacy of retigabine will be evaluated by comparison of baseline seizure frequency (obtained during the 8-week baseline period of Study VRX-RET-E22-302) with seizure frequency obtained during retigabine therapy in this study. The primary efficacy variable will be the percentage change in the monthly seizure rate from the baseline phase to open-label treatment. The proportion of responders (patients experiencing <math>\geq 50\%</math> reduction in seizure frequency) from baseline to the open-label treatment phase will also be evaluated.
 
• Safety: Safety will be assessed by measurements of vital signs, weight, clinical laboratory evaluations (blood chemistry, hematology, and urinalysis), 12-lead ECGs, physical and neurological examinations, and evaluations of adverse events. Patients will additionally be assessed using the American Urological Association Symptom Index to assess the urinary voiding function.
 

STATISTICAL ANALYSIS:
	
The safety population will include all patients who successfully complete the Transition phase of Study VRX-RET-E22-302 and were included in this long-term study. The Transition phase is the phase of Study VRX-RET-E22-302 during which patients were adjusted to a 300 mg TID dose of retigabine. No other population for analysis is defined for this long-term extension study.
 
Assessment of Efficacy:
 
"Monthly total partial seizure" as well as "monthly total seizure" rates will be calculated for the entire open-label part of Study VRX-RET-E22-304 and described statistically.
 
Baseline monthly total partial seizure rate from Study VRX-RET-E22-302 will be used for the calculation of difference and % change in the open-label study. The % change will be classified into <math><0</math>, <math>[0, 25)</math>, <math>[25, 50)</math>, <math>[50, 75)</math>, <math>[75, 100]</math> with a description of the frequencies. The responder rate (defined as a reduction in seizure frequency <math>\geq 50\%</math>) is the sum of the upper two classes.


STATISTICAL ANALYSIS (cont):
	
Assessment of Efficacy (cont):
 
The number of seizure free days, in percent to the individual duration of the open-label treatment, will be calculated and described statistically. In addition, frequencies for this percentage will be classified into [0, 25), [25, 50), [50, 75), [75, 95), [95,100), =100. The most upper class represents completely seizure free patients, the next class almost seizure free patients.
 
Additional details will be provided in the Statistical Analysis Plan (SAP).
 
Assessment of Safety:
 
All adverse events will be encoded according to MedDRA 8.0. Treatment emergent adverse events (TEAE) will be analyzed, i.e. all adverse events starting or worsening between the start of the long-term open-label study up to 30 days after end of taper-off study drug at the completion of the open-label study. Incidences on preferred term and body system basis will be calculated for all TEAEs. In addition, all serious adverse events (SAEs) and all AEs leading to premature discontinuation will be presented as separate listings. A prospective analysis will be conducted in order to compare the results of this study to Study VRX-RET-E22-302.
 
TEAE from both studies (double-blind and open-label extension) will be combined, i.e. each patient will be counted just once (with patient's respective TEAE).
 
Other safety evaluations, such as vital signs, laboratory variables, ECG variables, AUA symptom index will be analyzed descriptively.
 
Additional details will be provided in the Statistical Analysis Plan (SAP).

--	--

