### **9.4. Treatment Duration**

Following completion of the Transition Phase of the double-blind study (Study VRX-RET-E22-302), treatment in this open-label extension study will be continued until retigabine is approved and commercially available, or until the program is discontinued, followed by a 3-week tapering period and a 30 day post-study period for collection of adverse events.

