**10.15.9. Visit 14 (Month 48)**

Patients will return for Study Visit 14 (Month 48). At this visit, the following evaluations will be performed:

- Seizure Diary (collection / review of current diary and dispensation of new diary)
- Complete Physical and Neurological Exam
- Vital Signs (BP, HR, and Temperature) and Body Weight

- AUA Symptom Index
- PVR Bladder Ultrasound
- Clinical Laboratory Tests (Blood Chemistries, Hematology, Urinalysis including microscopy)
- Serum Pregnancy Test
- 12-lead ECG
- Adverse Events
- Concomitant Medication
- QOLIE-31-P Questionnaire (completed by patient)
- Open-Label Study Medication (collect returned medication and dispense new medication)

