### 4.3 General Considerations

Study day is defined as the number of days relative to Day 0 (i.e., the start of study treatment in the double-blind study VRX-RET-E22-302), computed as (the date – Day 0 date+1).

Continuous data that are assumed to be normally distributed will be summarized in terms of the mean, standard deviation (SD), median, minimum, maximum and number of observations. Continuous data that are expected to be skewed will be presented in terms of the maximum, upper quartile, median, lower quartile, minimum and number of observations. The minimum and maximum will be reported to the same number of decimal places as the raw data recorded in the database. The mean, SD, median, lower quartile and upper quartile will be reported to one more decimal place than the raw data recorded in the database. In general, the maximum number of decimal places reported shall be four for any summary statistic.

Categorical data will be summarized in terms of the number of patients providing data at the relevant time point (n), frequency counts and percentages. Percentages will be presented to one decimal place. Percentages will not be presented for zero counts. Percentages will be calculated using n as the denominator.

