### 4.5.2 Adverse Events

Adverse events (AEs) are monitored from the start of this extension study (informed consent provided by patient at the Baseline visit) until 30 days after administration of the last dose of study drug (end of study drug taper-off).

The AEs will be coded using the most recent Medical Dictionary for Regulatory Activities (MedDRA), Version 9.1. The number and percentage of patients experiencing at least one adverse event will be summarized overall and by body system and preferred term. In any given body system or preferred term patients will only be counted once. Adverse events will further be categorized and summarized by severity and study drug relationship. If the same event for a patient has two different severities, the worst will be taken.

Abnormal laboratory values do not themselves represent adverse events unless they:

- are indicative of a disease or defect, e.g. reduced hematocrit resulting in anemia;

- necessitate intervention, e.g., administration of packed red blood cells or other therapies; and
- result in dose reduction or permanent discontinuation of the drug product.

Worsening of seizure frequency will not be considered an AE but will be captured in the efficacy analysis. Those patients who discontinue their treatment prematurely either during the double-blind period or choose not to enter the open-label extension study should be tapered off their study treatment gradually and will be closely monitored by scheduled clinic visits for worsening of their seizure frequency during this period.

Adverse events will be graded for intensity. An intensity category of mild, moderate, or severe, is defined as

Mild	Causing no limitation of usual activities; the patient may experience slight discomfort
Moderate	Causing some limitation of usual activities; the patient may experience annoying discomfort
Severe	Causing inability to carry out usual activities; the patient may experience intolerable discomfort or pain.

Adverse events will also be graded, by the investigator, for relationship of the AE to study drug. A relationship to study drug category of not related, possible, probable, definite, is defined as

Not Related	No temporal association and other etiologies are likely the cause
Possible	Temporal association, but other etiologies are likely the cause. However, involvement of the study drug cannot be excluded.

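### AE summaries are crude patient percentages over open-ended, unequal follow-up, so they cannot support the planned comparison with Study 302 or show when AEs arise

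*Protocol*

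**What the plan says.** **Comparison and pooling.** The comparison appears in the Assessment of Safety paragraph of the protocol synopsis (section 6): "A prospective analysis will be conducted in order to compare the results of this study to Study VRX-RET-E22-302". The same part sets the AE measure, "Incidences on preferred term and body system basis will be calculated for all TEAEs", and plans a pooled count: "TEAE from both studies (double-blind and open-label extension) will be combined, i.e. each patient will be counted just once". Protocol 11.2 repeats the pooled count but not the comparison, and leaves the full safety methods to the SAP.

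**AE measure in the SAP.** SAP 4.5.2 says: "The number and percentage of patients experiencing at least one adverse event will be summarized overall and by body system and preferred term". The counting rule is "In any given body system or preferred term patients will only be counted once", and SAP 4.3 adds: "Percentages will be calculated using n as the denominator". SAP 4.5.3 treats fatal, serious and withdrawal-related events in the same way. Tables 15 to 21 contain nothing but n (%). The SAP has neither the Study 302 comparison nor the pooled count, yet SAP 4.8 reports no change to the planned analysis.

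**Follow-up.** Protocol 9.4 says that "treatment in this open-label extension study will be continued until retigabine is approved and commercially available, or until the program is discontinued". Amendment 2 schedules visits to Month 48 (Protocol 10.15.9). Study 302 has 4 weeks of titration and 12 of maintenance, plus a 4-week transition for patients entering the extension (Protocol 7.1). Extension exposure is summarised in Table 14 and is not linked to AEs.

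**The concern.** The percentage of patients who ever had an event rises with time observed, even when the risk per unit time is flat. It falls when patients leave early. Setting an extension percentage beside a Study 302 percentage therefore compares durations as well as risks.

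Long-term safety and tolerability is the primary objective (Protocol 8), and the AE tables have no time dimension. They cannot separate an event that occurs early and settles from one that accumulates over years. The plan already allows for unequal follow-up in efficacy, a secondary objective. SAP 4.4 standardises seizures to 28 days, relates seizure-free days to individual duration, and shows cohorts by minimum treatment duration.

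**Working it through.** **Plan's own figure.** There is none to reproduce. Neither document gives an AE rate for Study 302 or the extension, and Protocol 11.3 makes no sample size calculation.

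**Inputs from the documents**
- Study 302: 4 + 12 = 16 weeks = 112 days; 20 weeks = 140 days with transition (Protocol 7.1).
- Last scheduled visit: Month 48 at 30 days per month (Protocol 10.1) = 1440 days; 1440/365.25 = 3.94 years. The SAP, written to Amendment 1, tabulates to Month 36 = 1080 days.
- Earlier extension study (Protocol 7.4): median treatment 358 days; 18/222 = 8.1% discontinued within 3 months and 41/222 = 18.5% within 6 months.

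**Assumptions, not in the documents:** 16-week incidence p of 5% or 10%; constant hazard; exponential time on treatment.

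**Formulas.** Event hazard λ = −ln(1−p)/112 per day. Incidence for a patient followed t days = 1 − exp(−λt). Study-level crude incidence with dropout hazard μ, cut at T, is λ/(λ+μ) × [1 − exp(−(λ+μ)T)].

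**Step 1: one patient, unchanged risk**

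| Followed for | p = 5% | p = 10% |
|---|---|---|
| 30 days | 1.4% | 2.8% |
| 112 days | 5% | 10% |
| 358 days | 15.1% | 28.6% |
| 1440 days | 48.3% | 74.2% |

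**Step 2: whole study, unchanged risk.** μ = ln 2/358 = 0.001936.
- p = 5%: λ = 0.000458; 0.1913 × (1 − 0.0318) = 18.5%.
- p = 10%: λ = 0.000941; 0.3270 × (1 − 0.0159) = 32.2%.

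**Step 3: other dropout assumptions**

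| Dropout set from | Implied median | p = 5%, cut at Month 36 / 48 | p = 10%, cut at Month 36 / 48 |
|---|---|---|---|
| 358-day median | 358 days | 17.7% / 18.5% | 31.2% / 32.2% |
| 41/222 by 6 months | 611 days | 23.6% / 25.9% | 40.5% / 43.1% |
| 18/222 by 3 months | 738 days | 25.5% / 28.4% | 43.5% / 46.7% |

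**Step 4: patient-year measure.** λ × 36,525 gives 16.7 (p = 5%) and 34.4 (p = 10%) first events per 100 patient-years at risk. Under these assumptions the figure is the same in both studies, as it should be when risk is unchanged.

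**Step 5: where person-time is not enough.** Entrants must have completed Maintenance and Transition of Study 302 (Protocol 9.5). Patients who left earlier because of AEs are absent. Extension day 1 comes after 20 weeks in Study 302, and former placebo patients begin retigabine in Transition. Ongoing AEs are carried onto the extension CRF (Protocol 10.5), but SAP 4.5.2 counts only onset on or after the first extension dose, or worsening. For AEs concentrated in titration, all this can make the extension look safer than it is.

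**The case against.** The comparison is a single synopsis sentence. It speaks of results, names no measure, and is absent from Protocol 11.2 and from the SAP. A reader might infer that the sponsor has committed to comparing crude Table 15 percentages with Study 302. The documents do not say so. They show a planned comparison without a method, and AE tables that could not supply one. That is the defect claimed here.

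In a single-arm extension, n (%) is an ordinary description, and that stands. A reader might also infer that the plan has no view of safety over time. That goes too far: laboratory values, vital signs, ECG, neurological findings, AUA and PVR are tabulated by visit, and the AE listing carries the start study day. The gap is confined to the AE tables.

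Constant hazard is open to challenge, because Protocol 7.5 describes CNS events as dose-dependent and limiting dose increases, so early clustering is plausible. This stands, and it means that the direction of bias is not fixed. It also rules out a headline such as 1 − 0.9^(156/16) = 64%, which would need every patient to be followed for 156 weeks. Nor do the documents state exposure beyond four years: open-ended treatment permits it, but Month 48 is 3.94 years.

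Finally, a reader might take extension weeks 0 to 16 as a like-for-like match to Study 302. Step 5 shows why they are not.

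**Conclusion.** The point holds in this form: crude percentages are fine as description, but they cannot carry a comparison or pooled reading with Study 302, and they do not show when AEs arise. The SAP leaves both analyses without a method while stating that nothing changed.

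With risk unchanged, the illustrative distortion is roughly a factor of three or more: 5% becomes 18% to 28%, and 10% becomes 31% to 47%. These figures rest on assumed incidences, a constant hazard and exponential dropout borrowed from another study. They show scale and do not predict this trial's rates. The change should be made because it serves the primary objective and uses dates already collected.

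**What to change.** 1. Keep n (%) in Tables 15 to 21. Add patient-years, first events per 100 patient-years, and incidence by onset interval with patients at risk at the start of each interval as denominator.
2. Count extension person-time from the first extension dose. SAP 4.5.1 starts exposure at the first dose date, labelled Day 0, but SAP 4.3 defines Day 0 as the start of treatment in Study 302. Read that way, the denominator would include Study 302 time, some of it on placebo, while SAP 4.5.2 counts events only from the first extension dose.
3. Settle the Study 302 comparison. Either specify it with exposure-adjusted rates by time since first retigabine dose, restricted to or stratified by patients who entered the extension, with the selection caveat stated, or record its removal in SAP 4.8. Treat the pooled count likewise. Do not present extension weeks 0 to 16 as equivalent to Study 302.

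The cost is longer tables and one extra derived exposure variable. No new data are needed.
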